
 • To evaluate the efficacy of idasanutlin monotherapy: 
 – by Hct control without phlebotomy 	
 • Hct control is defined as protocol-specified ineligibility for phlebotomy between Week 8-Week 32 and ≤1 instance of phlebotomy eligibility between first dose and Week 8 
Definition of eligibility for phlebotomy: a Hct of ≥45% that was ≥ 3% higher than baseline level or a Hct of >48%

Secondary	

 • To evaluate the efficacy of idasanutlin monotherapy by complete hematologic response • To evaluate the efficacy of idasanutlin monotherapy by using modified ELN hematologic response criteria (complete and partial response) in patients with baseline splenomegaly, patients without baseline splenomegaly and in all patients irrespective of spleen size 	
 • Complete hematologic response at Week 32 
Complete hematologic response requires all of the following:
 
 – Hct control (protocol-specified ineligibility for phlebotomy between Weeks 8–32 and ≤1 instance of phlebotomy eligibility between first dose and Week 8); – White blood cell count ≤10 ×10⁹/L at Week 32 assessment; AND – Platelet count ≤400 ×10⁹/L at Week 32 assessment 
 • Complete hematologic remission at response Cycle 11 Day 28 defined as patients with all of the following: 
 – Hct control defined as protocol specified ineligibility for phlebotomy between Week 32 assessment and Cycle 11 Day 28 – White blood cell count ≤10 ×10⁹/L at Cycle 11 Day 28 assessment; AND – Platelet count ≤400 ×10⁹/L at Week 32 assessment • Duration of complete hematologic remission response with a durable responder defined as a subject in complete hematologic remission at Week 32 and Cycle 11 Day 28, as defined above • Response by using modified ELN hematologic response criteria: 
 – Complete response – Partial response – NR – Progressive disease, as defined by increased bone marrow fibrosis from baseline, and/or transformation to MF, MDS or acute leukemia • Duration of response, including proportion of patients with durable response lasting at least 12 weeks from Week 32 (Hct control, CHR, ELN 2009 response and composite response, if applicable)

Objectives	Endpoints

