Concurrent malignancy exceptions include: Curatively treated carcinoma in situ of the cervix, good-prognosis ductal carcinoma in situ of the breast, basal- or squamous-cell skin cancer, Stage I melanoma, or low-grade, early-stage localized prostate cancer. Any previously treated early-stage non-hematological malignancy that has been in remission for at least 2 years is also permitted.
13. Patients with active GI conditions (Crohn's disease, ulcerative colitis, diverticulosis associated colitis, and Behçet's disease).
14. Clinically significant toxicity (other than alopecia) from prior therapy that has not resolved to Grade ≤ 1 (according to the NCI CTCAE, v4.0) prior to Day 1 Cycle 1

CONCOMITANT MEDICATIONS

Permitted Medication

- Megestrol administered as an appetite stimulant is acceptable when the patient is enrolled in the study.
- Since nausea is a commonly reported adverse event in previous studies, *anti-emetic prophylaxis is mandatory prior to each cycle, unless otherwise agreed upon between the investigator and the Medical Monitor.*
- Phlebotomy can occur anytime if clinically warranted per institutional guidelines.
- Institutional guidelines for use of growth factor support, transfusions, and antibiotics should be followed with consideration for prohibited medications.

[figure not shown]
Prohibited Medication

- The use of HU or other therapy intended to treat PV (other than phlebotomy, aspirin and other supportive therapies) is not permitted while the patient is on study.
- The use of CYP2C8 substrates, inhibitors, or inducers; OATP1B1/3 substrates; or CYP3A4 inducers is prohibited during the study and for at least 7 days (for inhibitors and substrates) and 14 days (for inducers), respectively, prior to initiation of study treatment, unless otherwise specified. Note that CYP3A4 inhibitors are not excluded and OATP1B1/3 substrates with $t_{1/2}$ shorter than 1 day are allowed except during idasanutlin treatment and for 72 hours after the last dose of idasanutlin.

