7.1 DISCONTINUATION OF STUDY TREATMENT

Patient must discontinue study treatment if they experience any of the following:

- Pregnancy
- Unacceptable toxicity as determined by Investigator.
 - For cardiac changes:

If a clinically significant finding is identified (including, but not limited to QTcF ≥ 500 ms and/or an increase of ≥ 60 ms in QTcF from screening), the Investigator or qualified designee will determine if the patient can continue in the study and if any change in clinical management is needed. This review of the ECG printed at the time of collection must be documented. Any new clinically relevant finding should be reported as an AE.
- Any medical condition that the Investigator or Sponsor determines may jeopardize the patient's safety if he or she continues in the study.
- Investigator or Sponsor determines it is in the best interest of the patient.
- Disease progression at any point ([Appendix 1](#)).

Study treatment may be discontinued due to non-compliance (e.g., consistent failure to show up for scheduled visits) or if no evidence of clinical benefit in the form of lack of achieving a CR or PR per the ELN 2009 criteria, lack of achieving a Hct response or lack of decreased phlebotomy requirement at Week 32 assessment (see [Appendix 1](#)).

Patients who discontinue study treatment prematurely will be asked to return to the clinic for a study completion/early termination visit (see Section [8.9.3](#)) and may undergo follow-up assessments (see Section [8.9.4](#)). The primary reason for premature study treatment discontinuation should be documented on the appropriate eCRF. Patients

who discontinue study treatment prematurely for reasons other than progression or NR (withdraw prior to Week 32) may be replaced.

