9.2.2 Sample Size in Ruxolitinib-Resistant or Intolerant Patients

Approximately 20 efficacy-evaluable, ruxolitinib-resistant or intolerant patients will be enrolled in the initial phase of the study. Approximately 40 additional patients may be enrolled for further evaluation of safety and efficacy if warranted by results in the initial phase of the study and upon the discretion of the Sponsor, in a cohort expansion phase.

In this population, a Hct control rate of 30% is considered to be clinically meaningful. Observing a Hct control rate of 40% (8/20) would provide a posterior probability of 82% that the true rate is greater than 30%. Assuming a true Hct control rate of 40%, there is a 75% probability of observing at least 7 responders out of 20 patients.

From the initial phase, if the proportion of responders based on Hct control is above 30% in the ruxolitinib-resistant or intolerant cohort, the Sponsor may decide to enroll approximately an additional 40 patients with the goal of registration (expansion cohort), that would be considered the totality of available efficacy and safety data. The minimum sample size of 60 (40 patients from the expansion plus 20 patients from the initial phase) is expected to give sufficiently narrow confidence intervals. Based on a sample size of N = 60, the following table shows corresponding lower bounds of the two-sided 95% confidence interval for a range of potential observed response rates.

Table 9 *Lower Limit of Two-Sided 95% Confidence Interval for a Range of Potential Observed Response Rates based on a Sample Size of 60 Patients*

Observed Response Rate	Lower Limit of Two-Sided 95% Confidence Interval (exact Clopper-Pearson method)
35% (21/60)	23.1
40% (24/60)	27.6
45% (27/60)	32.1
50% (30/60)	36.8
55% (33/60)	41.6
60% (36/60)	46.5

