9.3 POPULATIONS FOR ANALYSES

For purposes of analysis, the following *two main populations (and combined populations)* will be described as defined in [Table 10](#):

- *Ruxolitinib-naïve patients*
- *Ruxolitinib-resistant or intolerant patients*

Additional populations may be defined in the Statistical Analysis Plan (SAP).

Table 10 Analysis Populations for Ruxolitinib-Naïve and Ruxolitinib-Resistant or Intolerant Patients

Description Analyses Per Population and Combined Populations	
Efficacy	Primary efficacy population consists of patients who have completed at least 32 weeks of treatment or withdrew prior to Week 32 due to NR or progressive disease. There will also be an early-look efficacy population consisting of patients who have completed at least 3 and/or 5 cycles.
Safety	All patients who received at least one dose of the study treatment, whether prematurely withdrawn from the study or not, will be included in the safety analysis.
PK	All patients who have received at least one dose of study treatment and who have data from at least one post-dose sample will be included in the PK analysis population. Patients will be excluded from the PK analysis population if they significantly violate the inclusion or exclusion criteria, deviate significantly from the protocol, or if data are unavailable or incomplete which may influence the PK analysis. Excluded cases will be documented together with the reason for exclusion. All decisions on exclusions from the analysis will be made prior to database closure.
Pharmacodynamic	All patients who had at least one pre-dose and one post-dose pharmacodynamic assessment will be included and analyzed.

ITT=intent-to-treat; NR=no response; PK=pharmacokinetic.

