9.4.2 Efficacy Analyses

The efficacy analyses will include all patients in the efficacy analysis populations as defined in [Table 10](#).

The primary analysis will be triggered by at least 20 efficacy-evaluable, ruxolitinib-naïve patients, or at least 20 efficacy-evaluable, ruxolitinib-resistant or intolerant patients. Primary, secondary, and exploratory endpoints (see [Table 3](#)) will be analyzed using listings and summary statistics as appropriate. No formal statistical model and no formal hypothesis testing are planned in this study.

Patients with missing assessments (hematology and/or splenic imaging) that prevent evaluation of efficacy endpoints will be considered NR. To be considered as having Hct control (absence of phlebotomy eligibility) between Week 8 and Week 32, the patient cannot miss more than one scheduled Hct assessment during this period.

A detailed description of the statistical methods that will be used for the efficacy analyses will be provided in the SAP.

Interim analyses may be performed to evaluate preliminary results and to confirm continuous positive benefit/risk profile (see Section 9.5).

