5.7 Efficacy Analysis

5.7.1 Primary endpoint Response rate: Hct Criteria

The primary endpoint will be evaluated based on *hematocrit control* on the following populations

- All Patients without prior ruxolitinib exposure without Splenomegaly
 - Response is defined HCT control i.e. ≤ 1 instance of phlebotomy eligibility between first dose and Week 8; and ineligibility for phlebotomy between week 8 and Week 32 based on CRF;
Definition of eligibility for phlebotomy: a Hct of $\geq 45\%$ that was $\geq 3\%$ higher than baNPseline level or a Hct of $> 48\%$.
- Patients without prior exposure to ruxolitinib with Splenomegally
 - Using composite:
 - HCT control
 - $\geq 35\%$ reduction in spleen volume (primary at Week 32) from baseline
- All patients without prior exposure to Ruxolinitib with or without splenomegally
 - HCT control
 - Using HCT control without phlebotomy Notes:

A summary table for the response rates will be provided (RSPT01). Only descriptive statistics are used. No formal testing is done in the study.

RSPT01

Overview of response rate
Primary Efficacy Evaluable Population {, subgroup}
Protocol: {base protocol}

Overall At Week 32	Ruxolitinib Naïve (N=xx)			Ruxolitinib Exposed (N=xx)			All Patients (N=xx)
	With Splenomegaly (N=xx)	Without Splenomegaly (N=xx)	All Patients (N=xx)	With Splenomegaly (N=xx)	Without Splenomegaly (N=xx)	All Patients (N=xx)	
HCT Control	xx (xx.x%)	xx (xx.x%)	xx (xx.x%)	xx (xx.x%)	xx (xx.x%)	xx (xx.x%)	xx (xx.x%)
95% CI	(x.xx, x.xx)	(x.xx, x.xx)	(x.xx, x.xx)	(x.xx, x.xx)	(x.xx, x.xx)	(x.xx, x.xx)	(x.xx, x.xx)
Not Evaluable (NE)	xx (xx.x%)	xx (xx.x%)	xx (xx.x%)	xx (xx.x%)	xx (xx.x%)	xx (xx.x%)	xx (xx.x%)
Missing	xx (xx.x%)	xx (xx.x%)	xx (xx.x%)	xx (xx.x%)	xx (xx.x%)	xx (xx.x%)	xx (xx.x%)
Composite Response %	NA	NA	xx (xx.x%)	NA	NA	xx (xx.x%)	xx (xx.x%)
95% CI	NA	NA	(x.xx, x.xx)	NA	NA	(x.xx, x.xx)	(x.xx, x.xx)
Not Evaluable (NE)	NA	NA	xx (xx.x%)	NA	NA	xx (xx.x%)	xx (xx.x%)
Missing	NA	NA	xx (xx.x%)	NA	NA	xx (xx.x%)	xx (xx.x%)

Patients were classified as "Not Evaluable" if all post-baseline response assessments were reported as not evaluable, or SD assessment occurring within xxx weeks from baseline/study entry.

Patients were classified as "Missing" if no post-baseline response assessments were available.

Notes

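### Prohibited PV therapy before Week 32 has no effect on response status, so a patient who stays on idasanutlin while taking it can be scored a responder

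*Protocol*

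**What the plan says.** The protocol Synopsis, and again Section 6.5.2, sets the ban: "The use of HU or other therapy intended to treat PV (other than phlebotomy, aspirin and other supportive therapies) is not permitted".

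The efficacy rules do not refer to it:

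- **Response definitions.** Hct control rests on phlebotomy eligibility, which is a rule on Hct values relative to 45%, 48% and baseline. Composite response adds spleen volume, and CHR adds WBC and platelets. ELN complete response also needs a normal spleen and no disease-related symptoms, and ELN progression rests on marrow fibrosis or transformation (protocol Table 3 and Appendix 1). SAP 5.7.1 repeats the Hct rule as "ineligibility for phlebotomy between week 8 and Week 32 based on CRF".
- **Analysis set (protocol Table 10).** "Primary efficacy population consists of patients who have completed at least 32 weeks of treatment or withdrew prior to Week 32" for no response or progression. There is no exclusion for prohibited therapy.
- **Imputation (protocol 9.4.2).** "Patients with missing assessments (hematology and/or splenic imaging) that prevent evaluation of efficacy endpoints will be considered NR". This is the only non-responder imputation, apart from the limit of one missed Hct assessment.
- **Stopping treatment (protocol 7.1).** The mandatory reasons do not name prohibited therapy. "Study treatment may be discontinued due to non-compliance", which is discretionary.
- **Deviations (SAP 5.3).** Major deviations are listed and summarized, with no effect on efficacy status.

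**The concern.** Cytoreductive drugs act on the quantities that define response here: Hct, WBC, platelets and spleen size. The trial is open-label with a single arm, so no control group absorbs the effect of an added drug. If the added drug changes a patient's status, it turns a failure into a response, so the error runs upward.

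An investigator can have a reason to add such a drug before the patient has failed. Protocol 2.2.1 gives Hct below 45% as the treatment aim, but failure is set higher. Reading the 3% margin as percentage points, a patient with baseline Hct 46% who reaches 48% is not phlebotomy-eligible, because 48 − 46 = 2 is below 3 and 48 is not above 48. WBC and platelets do not enter Hct control at all.

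At stake are the primary response rates and the initial-phase result that informs the expansion in ruxolitinib-resistant or intolerant patients, which is meant to support registration.

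**Working it through.** **Step 1: trace one patient through the rules.** Suppose a patient has no phlebotomy eligibility to Week 14, starts a prohibited PV drug then for a rising platelet count, continues idasanutlin, and has complete data with Hct controlled to Week 32.

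- Table 10: 32 weeks of treatment completed, so the patient is in the set.
- Hct control: no eligibility in Weeks 8–32 and at most one instance before Week 8, so the criterion is met.
- 9.4.2: no assessment is missing, so no imputation applies.
- Result: responder for Hct control, and for composite response or CHR if the spleen or count criteria are also met.

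Two variants come out differently. If Hct had reached eligibility between Weeks 8 and 32, the patient has already failed Hct control, composite response and CHR. If the patient is withdrawn before Week 32 for non-compliance (protocol 7.1 and 7.2), Table 10 is not met and the patient may be replaced.

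**Step 2: reproduce the plan's figure.** Section 9.2.2 gives a 75% probability of at least 7 responders in 20 at a true rate of 40%. Exact binomial: P(X ≥ 7 | n = 20, p = 0.40) = 0.750. It reproduces.

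**Step 3: effect of one reclassified patient.** N does not change; one responder becomes a non-responder.

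- Ruxolitinib-resistant or intolerant, n = 20: 1/20 = 5 points. 7/20 = 35% becomes 6/20 = 30%, which is not above 30%.
- Ruxolitinib-naive, n = 20: 14/20 = 70% (the case used in 9.2.1) becomes 13/20 = 65%. With a uniform prior (the plan states none), the posterior probability of a rate above 60% falls from 80.0%, matching the plan's 80%, to 65.1%.
- Ruxolitinib-naive with splenomegaly, n = 12: 6/12 = 50% becomes 5/12 = 41.7%, or 8.3 points.
- n = 60: the Clopper-Pearson lower limit is 32.1% at 27/60 (as in Table 9), 30.6% at 26/60 and 29.1% at 25/60. Two patients take it below the 30% called clinically meaningful.

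**Step 4: illustration of the effect on the 30% level.** Assume that a fraction f of patients who would fail on idasanutlin alone are turned into responders by prohibited therapy. The documents give no value for f; 0 to 10% is an assumption. The observed rate is q = p + (1 − p)f, and the quantity of interest is P(X ≥ 7 | 20, q).

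| True rate p | f = 0 | f = 5% | f = 10% |
|---|---|---|---|
| 20% | q = 0.200: 8.7% | q = 0.240: 18.4% | q = 0.280: 31.7% |
| 30% | q = 0.300: 39.2% | q = 0.335: 52.7% | q = 0.370: 65.5% |

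**The case against.** Several objections have force.

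- **The result is inferred.** Neither document says that such a patient is a responder. That is correct, and the point is worded accordingly. The SAP also refers, for data-cut detail, to a separate derivation-rules module that is not available here. But the response definitions in both documents are explicit, and they give the result in Step 1.
- **There is an exit.** Non-compliance can end treatment or study participation, and protocol waivers are not allowed. A patient withdrawn this way before Week 32 is not credited in the primary set. This stands, but it is discretionary and leaves untouched the patient who is kept on treatment.
- **The need is limited.** Phlebotomy is allowed at any time, and the protocol has its own dose-escalation route for poor control. All patients are HU-resistant or intolerant, so rescue by HU is less plausible. This stands in part. Part of the intolerance definition (inclusion criterion 6) is set at the HU dose that achieves a response, and other prohibited agents such as interferon-alpha or anagrelide remain possible.
- **Use would be visible.** Treatments are recorded on the eCRF and listed, and major deviations are reported. However, two of the three medication summary tables in SAP 5.8.7, those covering concomitant use, leave out PV medications. The targeted table in 5.8.8 shows growth factor, anti-emetics, dexamethasone and lorazepam. A listing does not correct a response rate.

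A reader might also infer that reaching 7/20 opens the expansion. Section 9.2.2 does not support that: "if the proportion of responders based on Hct control is above 30% in the ruxolitinib-resistant or intolerant cohort", the sponsor may decide to enroll more patients, with overall efficacy and safety also in view.

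**Conclusion.** The gap is real, in a limited form. The plan bans other PV-directed therapy but gives its use no consequence in scoring. The default is an upward error for patients who stay on idasanutlin to Week 32, start prohibited therapy before any phlebotomy eligibility in Weeks 8–32, and would otherwise have failed. Each adds 5 points in a cohort of 20.

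The total bias cannot be sized, because the frequency is unknown; Step 4 rests wholly on its assumed range. One might infer that every patient who breaches the ban is credited as a responder. The documents do not support that, given the withdrawal route and the failure rule described in Step 1. No sample-size figure checked here is wrong, and the study is descriptive, so no test is affected. The change should be made, because the 30% level in a cohort of 20 can turn on a single patient.

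**What to change.** This is a change to the analysis only; clinical management is untouched. Add to protocol 9.4.2 and SAP 5.7.1–5.7.2:

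- A patient who receives prohibited PV-directed therapy (not phlebotomy, aspirin or supportive therapy) between first dose and the Week 32 assessment is a non-responder for Hct control, composite response, CHR and ELN complete or partial response.
- A Week 32 responder who starts such therapy before Cycle 11 Day 28 is not a durable responder. This fits the existing definition, which uses status at those two times.
- The response rate without this rule is shown as a sensitivity analysis.

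Derive the flag from the concomitant-treatment eCRF pages already collected (protocol 6.5.1). The cost is a short addition to each document, one derivation and one extra row per response table. The downside is that reported rates may be slightly lower.

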1.2 SCHEMATIC OF STUDY DESIGN

An overview of the study design is shown in Figure 1.

Figure 1 Overview of Study Design

**Patients without measurable splenomegaly at baseline ^spleen imaging at end C5 only if <35% reduction at end C3
 †to be evaluated in ruxolitinib naive patients ‡MPN-SAF-TSS, EORTC QLQ-C30, PGIC †Bone Marrow biopsy every 6 cycles post week 32 per PI discretion in context of ELN CHR response

Initial phase

Ruxolitinib Naïve patients (up to 20)

Ruxolitinib resistant or intolerant patients (up to 20)

If favorable benefit/risk

Expansion phase

Ruxolitinib resistant or intolerant patients (additional 40, in total n=60)

1.3 SCHEDULE OF ACTIVITIES

The Schedule of Activities (SoA) is provided in [Table 1](#) and [Table 2](#).

All activities must be performed and documented for each patient. Patients will be closely monitored for safety and tolerability throughout the study. Patients should be assessed for toxicity prior to each dose; dosing will occur only if the clinical assessment and local laboratory test values are acceptable. If the timing of a protocol-mandated study visit coincides with a holiday and/or weekend that precludes the visit, the visit should be scheduled on the nearest following feasible date, with subsequent visits rescheduled accordingly. If this deviates more than ± 2 days from the planned visit, it must be agreed upon with the Medical Monitor.

Table 1 Overall Schedule of Activities

Cycle	Screening	Cycle 1							Cycle 2 and Cycle 3		Cycle 3	Cycle 4 and Beyond	Cycle 5	End of Cycle 8 (32 Weeks) and beyond ^{17,19}	Final Visit ¹⁴
		Up to Day 28	Day 1	Day 2	Day 3	Day 4	Day 5	Day 15	Day 22	Day 1		Day 15			
Assessments															
Informed Consent ¹	x														
Review Inclusion/Exclusion Criteria	x														
Demography	x														
Medical History	x														
Previous and Concomitant Treatments										x					
Cancer (PV) History	x														
Height	x														
Weight	x								x			x			x
Vital Signs ²	x	x					x	x	x	x		x			x
ECOG Performance Status ²	x	x					x	x	x	x		x			x
ECG 12-Lead ³	x	x	x				x		(x)						
Complete Physical Examination ^{2,4}	x	x					x	x	x	x		x			x
Adverse Events ⁵											x				
Rx Administration															
Idasanutlin administration ⁶		x	x	x	x	x				x			x		
Disease Assessment ⁷															
CT or MRI of Spleen ¹⁶	x											x		x	x

Table 1 Overall Schedule of Activities (cont.)

Cycle	Screening	Cycle 1							Cycle 2 and Cycle 3		Cycle 3	Cycle 4 and Beyond		Cycle 5	End of Cycle 8 (32 Weeks) and beyond ^{17,19}	Final Visit ¹⁴
		Day	Up to 28 Days	Day 1	Day 2	Day 3	Day 4	Day 5	Day 15	Day 22		Day 1	Day 15			
Symptom Assessment Form (MPN-SAF TSS) ^{19,21}		x								x ²³		x		x	x	x
EORTC QLQ -C30 ^{19,21}		x								x ²³		x		x	x	x
Patient Global Impression of Change (PGIC) ^{19,21}										x ²³		x		x	x	x
Bone Marrow Biopsy	x														x	x
Bone Marrow Aspirate	x														x	x
ELN Response/Hct Response ²⁰												x		x	x	x
Composite Response ^{16,17}												x		x	x	x
Histologic Response ¹⁷															x	x
Local Laboratory Assessments																
HBV, HCV, and HIV screening ⁹	x															
Hematology with differential ^{2,10}	x	x					x	x	x	x	x	x ²²	x	x ²²	x ²²	x
Serum chemistry, Liver function tests, and creatinine ^{2,11}	x	x					x	x	x	x	x	x ²²	x	x ²²		x
Erythropoietin (EPO) level ²	x	x													x	x
Iron ²	x	x													x	x
Urinalysis ²	x	x								x		x	x			x
Pregnancy Test ¹²	x									x			x			x
Bone marrow histology ^{8,17}	x														x	x
Cytogenetics ^{17,18,19}	x														x	x
Molecular Markers	x															

Table 1 Overall Schedule of Activities (cont.)

Cycle	Screening	Cycle 1							Cycle 2 and Cycle 3		Cycle 3	Cycle 4 and Beyond	Cycle 5	End of Cycle 8 (32 Weeks) and beyond ^{17,19}	Final Visit ¹⁴
Day	Up to 28 Days	Day 1	Day 2	Day 3	Day 4	Day 5	Day 15	Day 22	Day 1	Day 15	Day 28 ¹⁹	Day 1	Day 28 ¹⁹		EOS or 28 days post last dose
Central Laboratory Assessments															
PK idasanutlin ¹³	Refer to Additional Schedule of Assessments for specific Sample Collection Timepoint Details														
Serum MIC-1															
Nucleic Acid Whole Blood ¹⁵															
Paxgene Whole Blood															
Exploratory Biomarker pharmacodynamic Flow Blood															
Blood Flow Cytometry TBNK Panel															
Cytokine Assay															
RBR DNA															
RBR Serum															

AE=adverse event; COA=Clinical Outcome Assessment; CT=computed tomography; eCRF=electronic case report form; EORTC QLQ-C30=European Organization for Research and Treatment of Cancer Quality of Life Questionnaire–Core 30; EOS=end of study; HBsAg=Hepatitis B surface antigen; HBV=hepatitis B; Hct=hematocrit; HCV=hepatitis C; MPN-SAF TSS=myeloproliferative neoplasm symptom assessment form total symptom score; MRI=magnetic resonance imaging; PGIC=Patient Global Impression of Change; PI=principal investigator; PK=pharmacokinetic; PV=polycythemia vera; RBR=Research Biosample Repository; SAE=serious adverse event; TBNK=T, B, and NK.

- ¹ Informed consent must be obtained before any study-specific procedures. (Note: A separate consent form is required for RBR testing).
- ² If indicated assessments are performed within 72 hours before the first/next dose administration, the assessments do not have to be repeated on the first day of Cycle 1. If performed on the day of study drug administration they must be done PRIOR to study drug administration.

Table 1 Overall Schedule of Activities (cont.)

